**Table 4-3 Modified BOIN Decision Rules**

	Total Number of Subjects Treated at a Dose Level	2	3	4	5	6	7	8	9
Decision Based on Total Number of DLTs at the Dose Level	Escalate	0	0	0	$\leq 1$	$\leq 1$	$\leq 1$	$\leq 1$	$\leq 2$
	Remain	-	1	1	-	2	2	2	3
	De-escalate	1	2	2	2	3	3	3	4
	Terminate a dose level	$\geq 2$	3	$\geq 3$	$\geq 3$	$\geq 4$	$\geq 4$	$\geq 4$	$\geq 5$

**Table 4-4 Modified BOIN Decision Rules for AML Escalation Part**

	Total Number of Subjects Treated at a Dose Level	2	3*	4	5	6	7	8	9
Decision Based on Total Number of DLTs at the Dose Level	Escalate	0	0	0	0	$\leq 1$	$\leq 1$	$\leq 1$	$\leq 1$
	Remain	-	1	1	1	-	2	2	2
	De-escalate	1	2	2	2	2	3	3	3
	Terminate a dose level	$\geq 2$	$\geq 2$	$\geq 3$	$\geq 3$	$\geq 3$	$\geq 3$	$\geq 4$	$\geq 4$

\* For cohort sizes of 3 subjects the 3+3 run-in design is applied

#### **4.1.2.1 Stopping Rules**

The modified BOIN algorithm has the following stopping rules:

- i. The escalation in MM stops if there are 9 subjects already dosed on the next DL
- ii. The escalation in AML stops if there are 6 subjects already dosed on the next DL

These rules, and the planned number of DLs (6 and 3 for MM and AML, respectively), can be translated into an overall stopping rule for the mBOIN escalation that limits the number of subjects:

- iii. Escalation in MM stops if 54 subjects have already been dosed.
- iv. Escalation in AML stops if 18 subjects have already been dosed.

Further details on expected sample sizes are provided in Section 9.2.1.

At any time point in advance of this, the DEC and Safety Committee may conclude (given the totality of the accumulated data so far) on a RP2D for the expansion cohorts.

#### **4.1.2.2 Dose Level Termination**

A potential drawback of the basic BOIN design is that, theoretically, a very toxic DL could be investigated in multiple DLs, if a neighboring DL is not toxic. To avoid this problem, a DL termination criterion is implemented as a modification to the basic BOIN: A certain DL can no longer be investigated if an additional DLT-free cohort would lead to de-escalation. All higher DLs should also be terminated.

#### **4.1.2.3 Dose Escalation Cohort Size**

In the standard titration with 3 subjects per cohort, a recommendation based on Table 4-3 may be made in the following scenario: if 1 out of the 3 initial subjects on a new DL is non-DLT

evaluable and the remaining 2 are DLT-evaluable; provided that neither of the 2 subjects experienced any grade  $\geq 2$  non-hematologic toxicity excluding grade  $\leq 2$  IRRs, nor any DLT during the 28-day DLT period. (See Section 9.3 for a definition of DLT-evaluable.) In this example the BOIN would recommend an escalation. (It is not necessary to replace the non-DLT evaluable subject to proceed with the escalation.)

Also, over-recruitment by 1 subject is allowed, so that each 3-subject cohort may consist of 2 to 4 subjects who are evaluable for DLT.

In case a cohort had less than 3 DLT evaluable subjects, the next cohort on the same DL may be enlarged to bring the number of subjects on the DL up to a multiple of 3.

#### **4.1.2.4 *Parallel DL(s) for Clinical Confirmation***

To better understand the safety, tolerability, PK, pharmacodynamics, or anti-tumor activity, up to 7 additional subjects may be allocated in parallel to DLs that are considered safe for such allocation (DLs at or below the currently investigated one).

Any DLTs observed in such subjects will not directly contribute to the mBOIN design evaluation. However, if the mBOIN algorithm later stipulates de-escalation to an over-recruited DL, all subjects on that dose will be included in the mBOIN algorithm.

#### **4.1.2.5 *Determination of RP2D and MTD***

The principal objective of mBOIN is to optimize the move (de-escalate, remain, escalate), such that the (estimated) toxicity of the next DL is within the target toxicity range  $[\phi_1; \phi_2]$ . As data accumulate (towards the end of the dose escalation), the MTD, if reached, may be that next DL (no subjects are dosed at the next DL at this point).

The RP2D to be used for the Expansion Part A (GEN3014 Single Cohorts) and Expansion Part B (Randomized H2H) will be determined at the end of the Dose Escalation part by the DEC and Safety Committee, based on a review of the totality of data, including but not limited to safety (including DLTs, AEs, safety laboratory values, and observations made after the end of the DLT evaluation period), efficacy, PK and biomarker data, and dosing information. The RP2D may be the MTD (if reached) or a lower dose. The DEC and Safety Committee will strive towards alignment of the RP2D in the indications.

### 4.1.3 Expansion Part A (GEN3014 Single Cohorts)

In the Expansion Part A (GEN3014 Single Cohorts), there are 4 disease cohorts.

- Three cohorts of subjects will be treated with GEN3014 at the RP2D identified for RRMM from the Dose Escalation:
  - Anti-CD38 mAb-naïve RRMM (N=10 subjects). Data from the initial 10 response-evaluable subjects (defined in Section 9.3), inclusive of those anti-CD38 mAb-naïve subjects with RRMM who received GEN3014 at 16 mg/kg or 24 mg/kg from the Dose Escalation and/or from the Expansion Part A, will be reviewed by the Safety Committee and DMC when they have completed  $\geq 2$  cycles of treatment. If 2 or more (out of the initial 10) subjects respond to GEN3014, an H2H comparison to daratumumab SC will be initiated; see Sections 4.1.4 and 9.5.1. (Assessment of disease response will be conducted by the investigator in accordance with the IMWG 2016 Response Criteria.) The lead-in part may consist of more than 10 subjects to ensure exposure to at least 2 cycles of GEN3014 treatment.
  - Anti-CD38 mAb-refractory RRMM (N=20 subjects).
  - R/R DLBCL (N=up to 40 subjects). This cohort will include at least 15 R/R DLBCL subjects with  $>50\%$  CD38 expression. When the initial 20 response evaluable subjects have completed  $\geq 2$  cycles of GEN3014 treatment, an interim futility analysis will be conducted; see Section 9.5.2. Based upon the response at the interim futility analysis, an additional 20 subjects may be enrolled into this cohort for a total of 40 subjects.

See Sections 5.1.2 and 5.2.1 for inclusion and exclusion criteria.

- A fourth cohort of subjects with R/R AML (N=20 subjects) will be treated with GEN3014 at the RP2D identified for AML from the Dose Escalation. See Sections 5.1.2 and 5.2.1 for inclusion and exclusion criteria.

The administration schedule in Expansion Part A will be the same as in Dose Escalation (see Section 6.1.6.1).

#### 4.1.4 Expansion Part B (Randomized H2H)

If the preliminary efficacy and safety are judged to be favorable in the initial 10 anti-CD38 mAb-naïve subjects with RRMM who received 16 mg/kg or 24 mg/kg (in the Dose Escalation or Expansion Part A), approximately 80 anti-CD38 mAb-naïve subjects with RRMM will be randomized in a 1:1 ratio to receive:

- GEN3014 IV at the RP2D (N=40), or
- Daratumumab SC at the approved dose of 1800 mg (N=40)

The aim of the head-to-head comparison between GEN3014 IV and daratumumab SC is to evaluate the efficacy and maximum Cycle 3 Day 1 Ctrough level of study treatments in at least 40 subjects on each treatment arm. To ensure the collection of sufficient efficacy, PK, and safety data, after approximately 80 subjects are randomized, additional enrollment to either treatment arm can be implemented to replace:

- Subjects who are randomized but never receive the study treatment; and/or
- Subjects who discontinue the study treatment prematurely prior to the Cycle 3 Day 1 dosing

A maximum of 90 subjects will be treated.

The administration schedule will be the same as in the Dose Escalation (see Section 6.1), except that the first dose of daratumumab SC will not be split between Days 1 and 2.

Randomization will be stratified by body weight at baseline ( $\leq 70$  kg vs  $> 70$  kg), CCI [REDACTED]. See Sections 5.1.3 and 5.2.2 for inclusion and exclusion criteria.

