##### ***4.4.1.3 Expansion Part B (Randomized H2H)***

The estimated trial duration for an individual subject is 22 months, consisting of up to 21-day screening period, an estimated 4-month treatment period (the duration of treatment may vary for each subject), and an estimated 17-month post-treatment follow-up period (the duration of follow-up may vary for each subject).

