#### **6.4.2.2 Expansion Part A (GEN3014 Single Cohorts) and Part B (Randomized H2H)**

In the Expansion Part A (GEN3014 Single Cohorts), subjects will be assigned to 1 of the 4 cohorts: anti-CD38 mAb-naive RRMM, anti-CD38 mAb-refractory RRMM, R/R AML, or R/R DLBCL.

In the Expansion Part B (Randomized H2H), anti-CD38 mAb-naive subjects with RRMM will be randomized in a 1:1 ratio to receive either GEN3014 or daratumumab SC. Subjects will be assigned randomly to 1 of the 2 treatment groups based on a computer-generated randomization schedule prepared before the trial by or under the supervision of the sponsor. The randomization will be balanced by using randomly permuted blocks and will be stratified by body weight at baseline ( $\leq 70$  kg;  $> 70$  kg) CCI [REDACTED]. The IRT will assign a unique treatment code, which will dictate the treatment assignment and matching study drug kit for the subject. The requestor must use their own user identification and personal identification number when contacting the IRT and will then give the relevant subject details to uniquely identify the subject. In order to ensure 40 evaluable subjects in each treatment arm (see Section 4.1.4 and Section 9.2.3), the sponsor may replace subjects by arm rather than stratification factors, if justified.

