## **9.3 Populations for Analyses**

**Full Analysis Set (FAS):** The FAS and safety set are defined in the same way and will comprise all enrolled subjects who receive at least 1 dose of trial drug (GEN3014 or daratumumab SC). In case of any deviations from planned dosing, subjects will be treated as per actual dosing.

The FAS will be used to summarize efficacy and safety analyses.

**Response Evaluable Set (RES):** Comprises all subjects in the FAS that at the timing of data cutoff date (for any interim reporting of the ongoing data):

- have measurable disease at baseline;
- had  $\geq 1$  on-treatment disease assessment;
- have died within 60 days of first trial treatment without post-baseline disease assessment (these are included as non-responders)

**Safety Set:** See definition for FAS.

**Per-Protocol Set:** Not applicable

**Dose-Determining Analysis Set (DDS):** The DDS will include all FAS subjects in the Dose Escalation part who meet the minimum exposure criterion and have sufficient safety evaluations or experience a DLT during the first 28 days of dosing (ie, in Cycle 1).

A subject will meet the minimum exposure criterion if the subject receives 4 out of the 4 preplanned doses during the DLT period. (The 2 initial split doses in Day 1 and Day 2 account for 1 preplanned dose.)

**Pharmacokinetic Analysis Set 1 (PAS1):** The PAS1 will include all enrolled subjects who receive at least 1 dose of trial drug (GEN3014 or daratumumab SC) and who provide at least 1 evaluable PK sample.

**Pharmacokinetic Analysis Set 2 (PAS2):** The PAS2 will include all enrolled subjects who received all 8 weekly GEN3014 or daratumumab SC doses in Cycles 1 and 2 with the cumulative dose administered amounting to 80% to 125% of the planned dose and provided a predose PK blood sample on Cycle 3 Day 1.

**Immunogenicity Analysis Set (IAS):** The IAS will include all enrolled subjects who receive at least 1 dose of trial drug (GEN3014 or daratumumab SC) and have a baseline and at least 1 evaluable on-treatment ADA sample.

**Biomarker Analysis Set (BAS):** The BAS will include all enrolled subjects who receive at least 1 dose of trial drug (GEN3014 or daratumumab SC) and have at least 1 evaluable biomarker sample.

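### Part B states a Cycle 3 Day 1 trough comparison in at least 40 subjects per arm, but the 90-subject cap, the replacement rule and the PAS2 definition do not secure that number

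*Protocol*

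**What the plan says.** Protocol section 4.1.4 describes the aim of the randomised part as evaluating efficacy and the Cycle 3 Day 1 trough "level of study treatments in at least 40 subjects on each treatment arm". After about 80 subjects are randomised, it allows replacement of two groups. The first is anyone allocated to an arm who gets no dose at all. The second is early stoppers: "Subjects who discontinue the study treatment prematurely prior to the Cycle 3 Day 1 dosing".

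It then sets a limit: "A maximum of 90 subjects will be treated". Section 6.4.2.2 permits replacement by arm and gives the purpose: "In order to ensure 40 evaluable subjects in each treatment arm". Section 9.2.3 gives about 40 evaluable per arm and does not define evaluable.

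The trough comparison (section 9.4.6.1) uses PAS2. Section 9.3 limits PAS2 to subjects who "received all 8 weekly GEN3014 or daratumumab SC doses in Cycles 1 and 2", with 80% to 125% of the planned cumulative dose and a Cycle 3 Day 1 predose sample. ORR uses the FAS, which needs only one dose (protocol section 9.3, SAP section 5.3.1).

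The only duration figure for Part B is in section 4.4.1.3: "an estimated 4-month treatment period (the duration of treatment may vary for each subject"). SAP section 3 gives 40 per arm, with no replacement rule or cap.

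**The concern.** These statements are the only basis given for the size of the randomised part, which has no hypothesis and no power calculation. One number, 40 per arm, is made to serve two analyses with different requirements. ORR needs a treated subject. The trough ratio needs a subject who is still on treatment at week 9, has missed no weekly dose and has given the sample. Replacement is aimed at the second requirement but is limited by the cap, and it does not cover everyone whom PAS2 excludes. The trough ratio could therefore be reported on clearly fewer subjects than the protocol promises, after up to 10 further subjects have been treated as replacements.

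**Working it through.** **Inputs from the documents.** Target 40 per arm, 80 in total; cap 90 treated (section 4.1.4). Allocation: subjects "will be randomized in a 1:1 ratio to receive either GEN3014 or daratumumab SC" (section 6.4.2.2), so 45 per arm at the cap. Cycle 3 Day 1 is the start of week 9 (Table 6-1), 56 days after the first dose. Treatment estimate 4 months, taken here as 121.75 days.

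**The plan's own figure.** Neither 40 per arm nor the cap of 90 comes with an attrition or precision input, so neither can be re-derived. Working backwards, never-treated subjects do not use up a cap on treated subjects, so the spare places are 90 − 80 = 10. The retention required is 80/90 = 88.9%.

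**Retention implied by 4 months.** This step rests on assumptions: the document does not say whether 4 months is a mean or a median, and gives no distribution. For Weibull shape k (k = 1 is a constant hazard):

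- as a mean, S(56) = exp(−(56/s)^k), with s = 121.75/Γ(1 + 1/k)
- as a median, S(56) = 0.5^((56/121.75)^k)

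| Shape | S(56), mean | S(56), median | Reaching Cycle 3 Day 1, of 45 |
|---|---|---|---|
| 1 | 0.631 | 0.727 | 28.4 to 32.7 |
| 2 | 0.847 | 0.864 | 38.1 to 38.9 |
| 3 | 0.933 | 0.935 | 42.0 to 42.1 |

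**Chance of 40 in both arms.** Because subjects may be replaced by arm, the 10 spare places are shared. Enrolling each arm until it has 40 takes as many subjects as are needed for 80 successes overall, so the probability is P(Bin(90, p) ≥ 80).

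| True proportion reaching Cycle 3 Day 1 | Chance of 40 in both arms |
|---|---|
| 72.7% | below 0.1% |
| 80% | 1.9% |
| 85% | 19% |
| 88.9% | 58% |
| 90% | 71% |
| 95% | 99% |

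**Further loss to PAS2.** Section 6.6.3.1.2 says that a skipped dose is not made up and exempts Day 1 of a cycle from the skipping rule. That leaves 8 − 2 = 6 skippable weekly doses. With an assumed skip chance q per dose, the share qualifying is (1 − q)^6:

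- q = 1%: 0.99^6 = 0.941, a 6% loss; 40 who reach Cycle 3 Day 1 become 37.7
- q = 2%: 0.98^6 = 0.886, an 11% loss; 40 become 35.4

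Applied to the three shapes, q = 1% to 2% gives PAS2 of about 25 to 31, 34 to 37 and 37 to 40 per arm.

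**Effect on precision.** The 90% CI multiplies and divides the geometric mean ratio by exp(t(0.95, 2n−2) × SD × √(2/n)). With an assumed between-subject CV of 60%, SD = √ln(1.36) = 0.555. The factor is 1.23 at n = 40, 1.26 at n = 33 and 1.30 at n = 25.

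**The case against.** The strongest reply has four parts.

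- **Efficacy.** Section 4.1.4 names efficacy and trough together, so a reader might infer that the ORR comparison also falls short of 40. It does not. ORR is analysed in everyone who received a dose, and 40 to 45 treated per arm is achievable under the cap.
- **The duration estimate.** A reader might take 25 to 33 per arm as what the protocol's own figures deliver. The documents do not support that. The range needs a constant hazard and, at its lower end, an assumed skip rate. The 4-month figure says that duration may vary, is the same as the one given for RRMM in Dose Escalation and Part A, and was not offered as a survival parameter. If early stopping is rare (shape 3), the cap suffices for reaching Cycle 3 Day 1.
- **The skip rate.** It is not in the documents. At 0.5% per dose and shape 3, PAS2 would be 42.0 × 0.995^6 = 40.8 per arm.
- **Consequence.** The trough is a secondary, descriptive endpoint without a test, section 9.2.3 says approximately 40, and the loss of precision is modest.

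All four stand as limits on the point. None supplies the missing attrition assumption, and none removes the mismatch between PAS2 and the replacement list, which follows from the definitions without any duration assumption.

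**Conclusion.** Wrong as written, for the stated size of the trough comparison only. The cap tolerates at most 11.1% loss before Cycle 3 Day 1 (10 of 90), and the protocol gives no reason to expect so little. Even at exactly 88.9% retention, 40 in both arms is reached with a chance of only about 58%, before any PAS2 exclusion. Across the shapes considered, between 28 and 42 of 45 per arm reach Cycle 3 Day 1. At an assumed skip chance of 1% to 2% per dose, a further 6% to 11% leave PAS2 without being replaced. The 88.9% requirement and the gap between PAS2 and the replacement rule come directly from the documents. The expected counts depend on how the 4-month estimate is read, on the hazard shape and on the skip rate, and should be shown as a range. The ORR comparison is unaffected.

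**What to change.** In protocol sections 4.1.4, 6.4.2.2 and 9.2.3, and in SAP section 3, define the 40 per arm as treated subjects: the FAS, for ORR. For the trough ratio, replace the commitment to at least 40, or to ensuring 40 evaluable, with the expected PAS2 number per arm. Give the assumed attrition to Cycle 3 Day 1, the assumed dose-skipping rate, the resulting range and the expected width of the 90% CI.

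Leave the SAP's rules for best overall response and ORR unchanged. In particular, do not add an instruction to count early discontinuers as non-responders: SAP section 5.1.3 keeps responses recorded before progression or new therapy, and such an instruction would alter the primary endpoint.

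The cost is wording in two documents and no added enrolment. The drawback is that a stated figure becomes less favourable.

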#### 4.2 Trial Design Rationale

This trial is being conducted in 3 parts. The Dose Escalation is being conducted to identify the RP2D and the MTD (if reached), and to evaluate safety, and obtain preliminary efficacy of GEN3014 in subjects with RRMM and R/R AML. The Expansion Part A (GEN3014 Single Cohorts) is being conducted to evaluate clinical activity of GEN3014 together with safety, tolerability, PK, pharmacodynamics, and biomarkers. The Expansion Part B (Randomized H2H) is being conducted to evaluate the efficacy of GEN3014 as compared to daratumumab SC. Since GEN3014 carries the E430G mutation and binds a different epitope than daratumumab, it may result in therapeutic potential in daratumumab-naïve and daratumumab-refractory MM patients.

To this end, the sponsor will conduct a Dose Escalation followed by Expansion Part A (GEN3014 Single Cohorts) and Expansion Part B (Randomized H2H). These data will be used to inform future clinical development of GEN3014 in hematologic indications.

Escalation and de-escalation in the Dose Escalation will be guided by the mBOIN approach.

To collect further data on the safety, tolerability, PK, and anti-tumor activity, the selected RP2D from the Dose Escalation will be studied in Expansion Part A (GEN3014 Single Cohorts) and Expansion Part B (Randomized H2H). The Expansion Part A (GEN3014 Single Cohorts) will include 4 cohorts (ie, RRMM-anti-CD38 mAb-naïve, RRMM-anti-CD38 mAb-refractory, R/R DLBCL, and R/R AML) and Expansion Part B (Randomized H2H) will evaluate GEN3014 IV in comparison to daratumumab SC in RRMM. All data will inform further investigation.

#### **4.2.1 Rationale For Not Preselecting Subjects With DLBCL Based on Level of CD38 Expression in Dose Expansion Part A (GEN3014 Single Cohorts)**

CD38 is expressed in the majority of DLBCL patients with heterogeneous levels. From preclinical studies, it is known that especially the level of CD38 expression per tumor cell is a very important determinant for sensitivity of that tumor cell to HexaBody-CD38-induced tumor cell lysis. It is also important to note that the Salles study (Salles et al., 2019) referenced in Section 4.3.2 had a cutoff of >50% of tumor cells positive for CD38, whereas the biology of CDC and hexamerization indicates that density of the antigen is more important than the quantity of CD38-positive cells.

CCI

CCI

### **4.3 Dose and Schedule Rationale**

#### **4.3.1 Dose Escalation**

##### **4.3.1.1 Dose Escalation for RRMM**

The starting dose for the phase 1/2 clinical trial GCT3014-01 was based on an integrated evaluation of nonclinical pharmacology, PK and safety data, including a comparison against daratumumab as a benchmark (see GEN3014 IB for additional details).

GEN3014 binds to the same target as daratumumab and was shown to elicit the same effector mechanisms: CDC, ADCC, ADCCP, direct cell death through Fc crosslinking and inhibition of CD38 cyclase activity. Antibody therapeutics displaying 1 or more of these effector mechanisms, including rituximab, obinutuzumab, daratumumab, and isatuximab, are generally administered at high DLs without major safety concerns (Lokhorst et al., 2015; Maloney et al., 1994; Martin et al., 2019; Sehn et al., 2012a). In the phase 1 clinical trial in MM, daratumumab started to show signs of efficacy at 4 mg/kg (Lokhorst et al., 2015) while the optimal therapeutic dose was found to be 16 mg/kg (Lokhorst et al., 2015; Xu et al., 2017), at an estimated average receptor occupancy of 90% and 98%, respectively (Genmab data on file, CCI). No MTD was established with the dose ranging up to 24 mg/kg. Since its approval for RRMM in 2015 (US) and 2016 (EU), the main adversities associated with daratumumab at the therapeutic dose including sARRs and cytopenias have been well managed in the clinical setting. Given the similarity in effector mechanisms, GEN3014 is not expected to be associated with safety liabilities beyond those established for daratumumab.

Effective concentrations of GEN3014 were similar to daratumumab for the FcγR-mediated effector functions ADCC, ADCCP, and direct cell killing through Fc crosslinking (see GEN3014 IB). GEN3014 showed higher cyclase inhibition than daratumumab, while both compounds showed a comparable effect on hydrolase activity (see GEN3014 IB). Reduction in CD38

enzyme activity is not considered to pose a specific risk, as anti-CD38 antibody treatment intrinsically leads to a loss of CD38 in the tumor microenvironment. This was not associated with major adversities for daratumumab nor for isatuximab (Martin et al., 2019), which showed considerably stronger inhibition of both cyclase and hydrolase activity (see GEN3014 IB).

GEN3014 was designed to induce highly potent CDC in CD38-expressing tumor cells. GEN3014 induced dose-dependent CDC in 23 out of 27 tumor cell lines of MM, AML and B-NHL origin, with an EC50 that was a factor of 7 higher compared to daratumumab (see GEN3014 IB). A high degree of similarity was observed in concentration-response between cell lines and MM patient primary cells (see GEN3014 IB). The EC50 value depended on cell surface density of CD38, with higher concentrations required for effective CDC in cell lines with lower CD38 expression. The maximum cell lysis was also highly correlated with CD38 expression. GEN3014 and daratumumab showed similarly low activity in cell lines with low CD38 density and near-complete lysis in cells with high CD38, while at intermediate CD38 density GEN3014 outperformed daratumumab. In line with these findings, GEN3014 did not induce specific lysis of non-malignant cells expressing low levels of CD38 including leukocytes and erythrocytes from 4 out of 5 healthy donors, while some lysis of monocytes, T cells, and NK cells was observed in the fifth donor. The slight reduction in NK cells that was observed was comparable between GEN3014 and daratumumab (see GEN3014 IB). Thus, GEN3014 showed improved CDC activity in malignant cells compared to daratumumab while the activity in healthy cell populations with lower CD38 density remained largely unchanged. In the context of phase 1/2 starting dose setting, enhanced CDC was the only critical difference between GEN3014 and daratumumab identified across the range of in vitro and ex vivo pharmacology and safety studies.

Given the mild safety profile and manageable adversities associated with daratumumab up to high DLs, CDC in itself is not considered a major liability. Yet, the enhanced potency of GEN3014 to induce CDC warrants some level of precaution. Therefore, the starting dose for GCT3014-01 was defined as the dose giving rise to 1-week average plasma exposure equal to the EC50 for CDC in MM cell lines. The observed EC50 was divided by a factor 1.5 to account for the higher potency of the pilot batch CCI (that is representative of the current Good Manufacturing Process [GMP] manufacturing process) to induce CDC (see GEN3014 IB). The associated dose was derived by a PK model for GEN3014 that was scaled from a published population PK model for daratumumab (Xu et al., 2017) as described in the IB.

The relative contribution of the various effector mechanisms to the overall efficacy of GEN3014 is currently unknown. It is therefore unclear how the superior CDC will influence the relationship between dose and efficacy relative to daratumumab. Given that antibody therapeutics with the same mechanisms are generally administered at high DLs without major safety concerns, the escalation in MM after the first cohort will cover the same steps as shown in the daratumumab phase 1 trial GEN501.

The PK of GEN3014 is anticipated to be time dependent. The lysis of malignant cells over the course of treatment is expected to reduce the impact of target-mediated clearance, so that sufficient target saturation can be maintained with decreasing dosing frequency. Whether the superior CDC translates to a faster depletion of tumor cells compared to daratumumab is currently unknown. Therefore, a regimen is used similar to that for daratumumab monotherapy: weekly for two 28-day cycles (QW×8), biweekly for four 28-day cycles (Q2W×8), then monthly (Q4W). Intrasubject dose escalation applies to the MM-DL1 (ie, a lower starting dose escalating to a higher dose in 1 subject). The first dose at each DL will be split equally between 2 consecutive days to accommodate long infusion durations and to control anticipated infusion

reactions (ie, 50%/50% on D1/D2 and on D8/D9 for cohort MM-DL1; 50%/50% on D1/D2 for cohort MM-DL2 and beyond).

